3.1 INCLUSION CRITERIA

Subjects must meet all of the following inclusion criteria to be eligible for participation in this study:

1. Treatment naïve, histologically-confirmed diagnosis of Follicular Lymphoma (FL) Grade 1, 2, or 3a, or Small Lymphocytic Lymphoma (SLL).
2. Subjects must have measurable or evaluable disease, and must have documented evidence for requiring treatment (bulky disease (>5 cm), high LDH, B symptoms, threatened organ function, splenomegaly, cytopenias due to lymphoma, or effusions).
3. Adequate organ system function, defined as follows:
 - a. Absolute neutrophil count (ANC) $\geq 0.75 \times 10^9/L$. **Note:** No growth factors or transfusions are allowed to meet eligibility criteria.
 - b. Platelets $\geq 50 \times 10^9/L$. **Note:** No growth factors or transfusions are allowed to meet eligibility criteria.
 - c. Total bilirubin ≤ 1.5 times the upper limit of normal (ULN) with the exception of Gilbert's Disease and Autoimmune Hemolytic Anemia.
 - d. Alanine aminotransferase (ALT) and aspartate aminotransferase (AST) $\leq 2.5 \times$ ULN if no liver involvement or $\leq 5 \times$ the ULN if known liver involvement
 - e. Creatinine ≤ 2.0 mg/dL OR calculated creatinine clearance (as calculated by the modified Cockcroft-Gault formula using ideal body mass [IBM] instead of mass) ≥ 30 mL/min
4. ECOG performance status ≤ 1 .
5. Patients must be ≥ 18 years of age.
6. Ability to swallow and retain oral medication
7. Female patients who are not of child-bearing potential, and female patients of child-bearing potential who have a negative serum pregnancy test within 72 hours prior to initial trial treatment. Female patients of child-bearing potential and all male partners must consent to use a medically acceptable method of contraception throughout the study period and for 4 months after the last dose of either study drug.
8. Willingness and ability to comply with trial and follow-up procedures.

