10 SAFETY REPORTING AND ANALYSIS

10.1 SAFETY ANALYSES

The safety population will include all subjects who received any study medication. The safety endpoints will include:

- Incidence of AEs and AEs considered to be drug-related
- Incidence of Grade 3 and Grade 4 AEs
- Incidence of SAEs
- Laboratory values

The safety endpoints will be listed and/or summarized. No inferential statistical analyses will be performed. All subjects who have received at least one dose of ublituximab and/or umbralisib will be included in the safety population.

The analyses of safety will be based on the frequency of adverse events and their severity for subjects in each portion who received at least one dose of study treatment. Worst toxicity grades per subject will be tabulated for select adverse events and laboratory measurements by using NCI CTCAE criteria v4.0.

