10.4 ADVERSE EVENTS (AE'S) AND TREATMENT EMERGENT ADVERSE EVENTS (TEAE'S)

All AEs and SAEs occurring on study will be listed by subject. The frequency and percentages of subjects with treatment-emergent adverse events (TEAEs) will be tabulated by system organ class (SOC) and preferred term (PT), where treatment-emergent is defined as any AE that:

- Occurs after first dosing of study medication and through the end of the study or up through 30 days after the last dose of study treatment, or
- Is considered treatment-related regardless of the start date of the event, or
- Is present before first dosing of study medication but worsens in intensity or the investigator subsequently considers treatment-related.

TEAEs that are considered at least possibly related to study treatment will be tabulated as well as deaths, SAEs, and events resulting in treatment discontinuation.

AEs that occur after informed consent but before first dosing of study medication will not be summarized but will be listed.

At each level of summarization, a subject will be counted only once for each AE, SOC, or PT experienced within that level. In the summation for AE severity, within each level of AE, SOC, or PT experienced, the one with the highest severity will be included. In the summation for AE's relationship to the study drug, within each level of AE, SOC, or PT experienced, the one with the closest relationship to the study drug will be included.

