10.5.2 ABNORMAL LABORATORY VALUES AND VITAL SIGNS

The reporting of abnormalities of vital signs as adverse events should be avoided. Abnormalities of vital signs should not be reported unless any criterion for an SAE is fulfilled, the vital signs abnormalities cause the subject to discontinue study treatment, or the investigator insists that the abnormality should be reported as an AE. Abnormal laboratory results should be noted in the eCRF as an adverse event if they are associated with an overdose, require or prolong inpatient hospitalization, or are otherwise considered clinically significant by the investigator. If an abnormal laboratory value or vital sign is associated with clinical signs and/or symptoms, the sign or symptom should be reported as an AE, and the associated laboratory value or vital sign should be considered additional information that must be collected in the relevant eCRF. If the lab abnormality is a sign of a disease or syndrome, only the diagnosis needs to be recorded on the SAE Form or AE eCRF.

Clinical Laboratory Results will be summarized. Summary statistics for actual values and for changes from baseline will be tabulated for laboratory results by scheduled visit. Subjects with laboratory values outside of the normal reference range at any post-baseline assessment will be summarized, and graded per NCI CTCAE Version 4.0 when applicable. Subject incidence of abnormal lab results will be summarized by treatment group and maximum grade for each abnormal lab finding.

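### The laboratory incidence and worst-grade tables count any out-of-range post-baseline value without comparing it with the subject's baseline grade

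*Combined protocol and SAP*

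**What the plan says.** Section 10.5.2 plans three laboratory summaries:

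- By visit: "Summary statistics for actual values and for changes from baseline will be tabulated for laboratory results by scheduled visit".
- By subject, out of range: "Subjects with laboratory values outside of the normal reference range at any post-baseline assessment will be summarized, and graded per NCI CTCAE Version 4.0".
- By subject, worst grade: "Subject incidence of abnormal lab results will be summarized by treatment group and maximum grade for each abnormal lab finding".

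Section 10.1 adds: "Worst toxicity grades per subject will be tabulated for select adverse events and laboratory measurements by using NCI CTCAE criteria v4.0".

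Only the by-visit summary refers to baseline. No table of baseline grade against worst post-baseline grade is planned anywhere in the document.

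For adverse events the plan does use baseline. Under section 10.4 a pre-existing event is treatment-emergent if it "Is present before first dosing of study medication but worsens in intensity or the investigator subsequently considers treatment-related".

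Section 3.1 shows which abnormalities subjects may bring into the trial. High LDH is among the accepted reasons for needing treatment, and the list ends with "threatened organ function, splenomegaly, cytopenias due to lymphoma, or effusions". The entry limits are:

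- ANC of at least 0.75 × 10⁹/L and platelets of at least 50 × 10⁹/L;
- ALT and AST up to 2.5 × ULN, or 5 × ULN with liver involvement;
- bilirubin up to 1.5 × ULN, with Gilbert's disease and autoimmune hemolytic anemia excepted;
- creatinine up to 2.0 mg/dL, or higher if calculated clearance is at least 30 mL/min.

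No hemoglobin limit is listed.

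**The concern.** A subject who enters with a permitted abnormality and stays at the same grade is counted at that grade. A subject whose value improves but is still out of range at the first post-baseline draw is also counted. High LDH and lymphoma-related cytopenia are themselves grounds for treatment, so such subjects are expected.

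Safety is a secondary objective, and laboratory values are a listed safety endpoint in section 10.1. In a single-arm trial nothing in these tables separates what subjects brought with them from what arose on treatment. A reader of the neutrophil, platelet or transaminase rows could take the whole count as treatment-emergent.

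**Working it through.** The plan gives no figure on this point, so there is none to reproduce. The check is a comparison of the rules, followed by an illustration.

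**Comparison of the rules**

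| Summary | Section | Uses the subject's baseline? |
|---|---|---|
| Actual values and change, by visit | 10.5.2 | Yes, but as group statistics |
| Any out-of-range post-baseline value, graded | 10.5.2 | No |
| Incidence by maximum grade | 10.5.2 | No |
| Worst toxicity grade, laboratory measurements | 10.1 | No |
| Treatment-emergent adverse events | 10.4 | Yes: worsening or investigator-judged relatedness |

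A by-visit mean or median change does not say which subjects moved up a grade, and it leaves the counts in the next three rows as they are.

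**Illustration: inputs**

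- N = 50, the planned maximum (section 4.1).
- b = share out of range at baseline. Assumed.
- e = share who newly develop an abnormality or worsen by at least one grade, taken as equal in those normal and abnormal at entry. Assumed.
- s = chance that an entry abnormality that does not worsen is still out of range at one or more post-baseline visits. Assumed.

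**Formulas**

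- Tabulated under the written rule: (1 − b)e + b[e + (1 − e)s] = e + b(1 − e)s.
- Tabulated under a treatment-emergent rule: e.
- Excess: b(1 − e)s.

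**Central case, b = 20%, e = 10%**

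- s = 0.5: 0.10 + 0.20 × 0.90 × 0.5 = 0.19.
- s = 1.0: 0.10 + 0.20 × 0.90 × 1.0 = 0.28.
- Treatment-emergent: 0.10.

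In 50 subjects that is 9.5 to 14 counted, against 5.

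**Varying b, with e = 10%**

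| b | Tabulated, s = 0.5 | Tabulated, s = 1.0 | Treatment-emergent |
|---|---|---|---|
| 10% | 14.5% | 19.0% | 10% |
| 20% | 19.0% | 28.0% | 10% |
| 30% | 23.5% | 37.0% | 10% |
| 40% | 28.0% | 46.0% | 10% |

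**Wider range, b = 10–40%, e = 10–30%, s = 0.5–1.0**

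- Smallest excess: 0.10 × 0.70 × 0.5 = 0.035, or about 2 of 50 subjects.
- Largest excess: 0.40 × 0.90 × 1.0 = 0.36, or 18 of 50.

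The excess b(1 − e)s cannot be negative. Read as a count of treatment-emergent abnormality, the written rule can therefore only overstate it.

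These figures concern incidence at any grade. The CTCAE cut-points are not printed in the documents, so no baseline grade is assigned to the eligibility limits and nothing is claimed about the size of the effect on the Grade 3 and 4 rows.

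**The case against.** The strongest reply is that baseline is already handled where it matters. Clinically significant laboratory results are recorded as adverse events (sections 10.5.2 and 10.9.2). A pre-existing condition is an adverse event only if it worsens (section 10.9.5), and section 10.4 applies its own test before an event is treatment-emergent. Section 10.5.2 labels its tables as abnormal results and does not call them drug effects. Section 10.1 rules out inferential safety analysis, section 9.2 promises listings of all safety data, and section 9 defers derivations to a formal SAP.

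Much of this stands, and it limits the point. Several stronger readings are tempting but not supported:

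- *Laboratory data are analyzed with no regard to baseline.* Not so; section 10.5.2 plans changes from baseline by visit.
- *The adverse event tables are inflated in the same way.* Not so; section 10.4 requires worsening or investigator-judged relatedness for pre-existing events.
- *The extra counts are disease-related.* The documents support only pre-existing. Gilbert's disease or a raised creatinine need not be due to lymphoma.
- *Safety decisions would be affected.* Section 4.2 gives the run-in its own definition of unacceptable toxicity, and no rule uses these tables.
- *In the central case the contrast is 28% against 8%.* The 8% would be 0.80 × 0.10, which gives subjects abnormal at entry no chance of worsening. The 28% assumes that every entry abnormality persists.

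The reply does not repair the tables themselves. A laboratory result becomes an adverse event only through overdose, hospitalization or the investigator's judgment of clinical significance. The laboratory tables are the systematic summary that does not depend on that judgment, and section 10.1 does call its worst grades toxicity. Listings let a reader reconstruct shifts by hand but do not summarize them. The formal SAP is not among these documents. It could add the definition, which is a reason to raise the point before it is finalized.

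**Conclusion.** The point holds for the laboratory incidence and maximum-grade tables in section 10.5.2 and the worst-grade laboratory tabulation in section 10.1, and for nothing wider. As written, they mix abnormalities present at entry with those that arise or worsen on treatment, in a population whose eligibility criteria admit such abnormalities and with no control arm.

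The direction follows from the text; the size does not. With 20% abnormal at entry, 10% newly abnormal or worsened, and 50% to 100% persistence of the rest, the tables show 19% to 28% where the treatment-emergent figure is 10%. All three rates are assumptions, as is the same worsening rate in subjects normal and abnormal at entry. The tables are descriptive and no trial decision rests on them, so this is a free improvement to the safety reporting and not a threat to the trial's conclusions.

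**What to change.** In sections 10.1 and 10.5.2, and in the formal SAP:

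1. Define a treatment-emergent laboratory abnormality as a post-baseline CTCAE grade at least one grade worse than the last pre-dose value.
2. Tabulate the maximum treatment-emergent grade per subject for each laboratory parameter.
3. Add tables of baseline grade by worst post-baseline grade.
4. If wanted, keep the existing any-abnormality summary beside these, labeled as including abnormalities present at entry.

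The cost is a few extra tables and some wording. The schedule in section 5 already collects hematology and chemistry at screening within 7 days of starting treatment. Cycle 1 Day 1 samples are taken before dosing, and the footnotes waive repeats when the initial tests fall within 72 hours of that day. A last pre-dose value should therefore exist without any new data collection.

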10.5.3 HANDLING OF ADVERSE EVENTS

All adverse events resulting in discontinuation from the study should be followed until resolution or stabilization. Subjects should be followed for AEs for 30 calendar days after discontinuation or completion of protocol-specific treatment (umbralisib or ublituximab). All new AEs occurring during this period must be reported and followed until resolution unless, in the opinion of the investigator, these values are not likely to improve because of the underlying disease. In this case, the investigators must record his or her reasoning for this decision in the subject's medical record and as a comment on the eCRF. After 30 days, only AEs, SAEs, or deaths assessed by the investigator as treatment related are to be reported.

10.6 SERIOUS ADVERSE EVENTS

10.6.1 DEFINITIONS OF SERIOUS ADVERSE EVENTS

The definitions of serious adverse events (SAEs) are given below. The investigator is responsible for ensuring that all staff involved in the study are familiar with the content of this section.

An SAE or reaction is defined as any untoward medical occurrence that:

- results in death, is immediately life-threatening,
- requires at least a 24-hour in-patient hospitalization or prolongation of existing hospitalization,
- results in persistent or significant disability/incapacity, and/or
- causes a congenital anomaly/birth defect.

Medical and scientific judgment should be exercised in deciding whether expedited reporting is appropriate in other situations, such as important medical events that may not be immediately life-threatening or result in death or hospitalization, but may jeopardize the subject or may require intervention to prevent one of the other outcomes listed in the previous definition. These should also usually be considered serious. Examples of such events are intensive treatment in an emergency room or at home for allergic bronchospasm; blood dyscrasias or convulsions that do not result in hospitalization; or development of drug dependency or drug abuse.

Progression of malignancy (including fatal outcomes), if documented by use of appropriate method (for example, as per Cheson et al. 2007, should not be reported as a serious adverse event.

A suspected unexpected serious adverse reaction (SUSAR) is defined as an SAE that is suspected to be at least possibly related to study medication(s) and is an unexpected event. SUSAR reporting is encompassed within SAE reporting guidelines as defined in this section.

Treatment within or admission to the following facilities is not considered to meet the criteria of "in-patient hospitalization" (although if any other SAE criteria are met, the event must still be treated as an SAE and immediately reported):

- Emergency Department or Emergency Room
- Outpatient or same-day surgery units

- Observation or short-stay unit
- Rehabilitation facility
- Hospice or skilled nursing facility
- Nursing homes, Custodial care or Respite care facility
- Admission for study related treatment

Hospitalization during the study for a pre-planned surgical or medical procedure (one which was planned prior to entry in the study), does not require reporting as a serious adverse event to the Sponsor.

10.6.2 SERIOUS ADVERSE EVENT REPORTING BY INVESTIGATORS

It is important to distinguish between “serious” and “severe” adverse events, as the terms are not synonymous. Severity is a measure of intensity; however, an AE of severe intensity need not necessarily be considered serious. For example, nausea which persists for several hours may be considered severe nausea, but may not be considered an SAE. On the other hand, a stroke which results in only a limited degree of disability may be considered only a mild stroke, but would be considered an SAE. Severity and seriousness should be independently assessed when recording AEs and SAEs on the eCRF.

Adverse events classified by the treating investigator as **serious** require expeditious handling and reporting to the Sponsor in order to comply with regulatory requirements. Serious adverse events may occur at any time after signing of informed consent through the 30-day follow-up period after the last study treatment. Sponsor or designee should be notified of all SAEs, regardless of causality, within 24 hours of the first knowledge of the event by the treating physician or research personnel.

To report an SAE, see the appropriate form.

All SAEs (regardless of causality assessment) occurring on study or within 30 days of last study treatment should be immediately reported to the sponsor as SAEs within the CRF and followed until resolution (with autopsy report if applicable).

Disease progression or death due to disease progression should be reported by the investigator as a serious adverse event only if it is assessed that the study drugs caused or contributed to the disease progression (i.e. by a means other than lack of effect). Unrelated events of disease progression should be captured on the appropriate eCRF.

The investigator must review and sign off on the SAE data on the SAE report. The SAE should be reported to the Sponsor (or Sponsor designee) as outlined in the Safety Monitoring Plan.

When an SAE is reported to the sponsor or designee, the same information should be entered on the eCRF within 24 hours (1 business day). Transmission of the SAE report should be confirmed by the site personnel submitting the report.

Follow-up information for SAEs and information on non-serious AEs that become serious should also be reported to the sponsor or designee as soon as it is available; these reports should be submitted using the appropriate SAE form.

Investigators must report SAEs and follow-up information to their responsible Institutional Review Board (IRBs)/Independent Ethics Committee according to the policies of the responsible IRB (Research Ethics Committee).

10.7 SPONSOR SAE REPORTING REQUIREMENTS

Sponsor is responsible for reporting relevant SAEs to the competent authority, other applicable regulatory authorities, and participating investigators, in accordance with ICH guidelines, FDA regulations, and/or local regulatory requirements.

Sponsor is responsible for reporting unexpected fatal or life-threatening events associated with the use of the study drugs to the regulatory agencies and competent authorities within 7 calendar days after being notified of the event. The Sponsor will report all related but unexpected SAEs including non-death/non-life-threatening related but unexpected SAEs (SUSAR) associated with the use of the study medications to the regulatory agencies and competent authorities by a written safety report within 15 calendar days of notification. Following the submission to the regulatory agencies and competent authorities, Investigators and trial sites will be notified of the SUSAR. Investigators must report SUSARs and follow-up information to their responsible Institutional Review Board (IRBs)/Independent Ethics Committee according to the policies of the responsible IRB (Research Ethics Committee).

10.8 RECORDING OF ADVERSE EVENTS AND SERIOUS ADVERSE EVENTS

Investigators should use correct medical terminology/concepts when recording AEs or SAEs on the SAE Report Forms and AE eCRF. Avoid colloquialisms and abbreviations.

All AEs, including those that meet SAE reporting criteria, should be recorded on the AE eCRF; AEs that meet the definition of an SAE should additionally be reported.

10.9 DIAGNOSIS VS. SIGNS AND SYMPTOMS

All AEs should be recorded individually in the subject's own words (verbatim) unless, in the opinion of the Principal Investigator or designated physician, the AEs constitute components of a recognized condition, disease, or syndrome. In the latter case, the condition, disease, or syndrome should be named rather than each individual sign or symptom. If a constellation of signs and/or symptoms cannot be medically characterized as a single diagnosis or syndrome at the time of reporting, each individual event should be recorded as an AE or SAE as appropriate on the relevant form(s) (SAE Report Form and/or AE eCRF). If a diagnosis is subsequently established, it should be reported as follow-up information is available. If a diagnosis is determined subsequent to the reporting of the constellation of symptoms, the signs/symptoms should be updated to reflect the diagnosis.

10.9.1 PERSISTENT OR RECURRENT ADVERSE EVENTS

A persistent AE is one that extends continuously, without resolution, between subject evaluation time points. Such events should only be recorded once on the SAE Report Form and/or the AE eCRF. If a persistent AE becomes more severe (changes from a Grade 1 or 2 AE to a Grade 3 or 4 AE) or lessens in severity (changes from a Grade 3 or 4 AE to a Grade 1 or 2 AE), it should be recorded on a separate SAE Report Form and/or AE eCRF.

A recurrent AE is one that occurs and resolves between subject evaluation time points, and subsequently recurs. All recurrent AEs should be recorded on an SAE Report Form and/or AE eCRF for each recurrence.

10.9.2 ABNORMAL LABORATORY VALUES

Abnormal laboratory results should be noted in the eCRF as an adverse event if they are associated with an overdose, require or prolong inpatient hospitalization, or are otherwise considered clinically significant by the investigator. If an abnormal laboratory value or vital sign is associated with clinical signs and/or symptoms, the sign or symptom should be reported as an AE, and the associated laboratory value or vital sign should be considered additional information that must be collected in the relevant eCRF. If the laboratory abnormality is a sign of a disease or syndrome, only the diagnosis needs to be recorded on the SAE Report Form or AE eCRF.

